1.0 Objectives / Specific Aims

The overall goal of this study is to assess maternal vitamin D status along with diet, and milk composition to, in turn, evaluate if infant vitamin D status can be improved with increased maternal supplementation and diet education. Our **central hypothesis** is that by maximizing maternal vitamin D status, there will be an increase infant 25(OH)D concentration in breastfed, preterm infants. This hypothesis will be tested by performing the following Specific Aims.

Aim 1: Determine the efficacy, effectiveness, and safety of maternal and premature infant vitamin D supplementation as a function of maternal vitamin D status, lactation status, and ethnicity.

H₁: Maternal supplementation of high dose (6,600 IU) vitamin D₃/day will be safe for lactating mothers.

H₂: It is anticipated that only high dose (6,600 IU) vitamin D₃/day supplementation of lactating mothers will provide sufficient antirachitic activity in breast milk to prevent vitamin D deficiency in nursing premature infants, regardless of ethnicity/race.

H₃: High-dose maternal supplementation will be safe and more effective than infant vitamin D supplementation alone, without any adverse side effects or health consequences in the mother or infant.

Consented lactating women who delivered preterm infants <35 weeks' gestation admitted to the MUSC NICU will be randomized 3-7 days following delivery to either 1 of 2 study groups: Group A (standard therapy of 600 IU vitamin D₃/day), Group B (high dose supplementation of 6,600 IU Vitamin D₃/day). As such, infants whose lactating mothers are randomized to the 600-IU/day group will receive 400-IU/day oral vitamin D₃ (recommended practice). Those infants of lactating mothers assigned to Group B will receive placebo. Calcium homeostasis will be monitored in all groups. Safety will be assessed throughout the study on a case-rather than a treatment arm basis using cautionary levels as the stop rule with intervention prior to exceeding normal urinary calcium/creatinine ratios in mothers and serum calcium concentrations in both mothers and infants. Through these proposed studies, the prevalence of vitamin D deficiency among mothers and their infants, and the utility of maternal therapeutic intervention with vitamin D₃ will be assessed.

Aim 2: Aim 2: Evaluate and maximize maternal milk composition.

For this aim, we will obtain maternal food dietary intake using the Diet History Questionnaire III (DHQ III). This is a validated tool that is based on a 24-hour dietary recall database from the National Health and Nutrition Examination Surveys (NHANES) in people 19 and older. This survey will be administered between post-partum days 3-7 at the time a milk sample is obtained and at 1-, 2-, and 3-month visits. We then will utilize a milk composition analyzer (name, city, state) in MUSC's Milk Bank to evaluate maternal milk sample composition at the initial visit and again at 1, 2 and 3 months of infant age. Prior to discharge from the NICU, the infant will undergo a body mass analysis using the PEA POD and Bone ultrasound. Analysis will be performed on maternal diet, milk composition, infant body

composition, and vitamin D status for any correlations. Samples will also be archived for metabolomics and cytokine analysis.

2.0 Background

Human milk remains the favorable form of nutrition for the neonate and infant (1). Neonatal vitamin D stores are inversely related to gestational age (2). Along with this, two-thirds of fetal calcium is accumulated in the third trimester. Postnatal risk factors for vitamin D deficiency (VDD) of preterm neonates include decreased sunlight exposure, difficulties with adequate enteral nutrition, and higher requirements for vitamin D. All these factors along with use of diuretics and steroids, lead to an increased risk. Many studies have shown the importance of vitamin D in neonatal and infant health. Munshi et al. found that 80% of ELBW and VLBW infants at Albany Medical Center were deficient or insufficient in vitamin D at 1 month of age (3). Along with deficiency, the incidence of metabolic bone disease is still elevated at 32% of VLBW and 54% of ELBW (4, 5). There is also a significant association between respiratory distress syndrome (RDS) and vitamin D deficiency, especially in infants \leq 30 weeks(6).

Maternal breast milk is the recommended source of nutrition for both full and preterm infants; however, if mother is deficient in vitamin D, her milk provides limited vitamin D, with roughly 3-4 IU/kg/day provided (7, 8). It has also been found that mothers and their preterm infants were more likely to be vitamin D deficient than mothers and their infants who carried to term. To further worsen this, those preterm infants who are not fed mother's own milk (MoM) are given donor breast milk. Unfortunately, through pasteurization there is 10-20% less vitamin D (9).

Maternal vitamin D status as measured by total circulating 25(OH)D concentration is influenced by many factors including ethnicity, season, high BMI, gestational diabetes, socioeconomic status (poor diet), and prenatal intake (10). From an ethnicity standpoint, African American, Middle Eastern, and Asian women are at highest risk for vitamin D deficiency. To no surprise, these are also the populations at increased risk of preterm delivery. In South Carolina in 2010, our group showed that vitamin D deficiency [defined as 25(OH)D <20 ng/mL (50 nmol/L)] was around 48% overall, with 68.3% of African-American women being deficient (11). In our NICHD vitamin D supplementation trial, there were similar findings with significant deficiency in African American and Hispanic women at baseline (12).

There are several studies evaluating various supplementation regimens in preterm infants; however, considerable attention has not been given to the role of maternal vitamin D supplementation and its effects on preterm neonate's vitamin D status. Many groups have recommendations on vitamin D supplementation that have failed to form a consensus or have differing recommendations for preterm neonates. The AAP Committee on nutrition recommends 200-400 IU of vitamin D for very low birthweight infants (VLBW). On the other hand, the European Society of Pediatric Gastroenterology and Nutrition (ESPGAN) recommends 800-1600 IU daily (13). Due to the lack of substantial data, these various groups fail to make recommendations on arguably those at highest risk--preterm, very low birthweight (VLBW) infants, and extremely low birthweight (ELBW) infants. Along with variations in supplementation recommendations, there are also variations among scientific groups as to an ideal target 25(OH)D level. The AAP recommends 25(OH)D > 20 ng/mL (50 nmol/L) (14) and in the same year another group published a paper with recommended 25(OH)D > 30 ng/mL (75 nmol/L) (15). The Endocrine Society targets >30 ng/mL (75 nmol/L) (16) while ESPGAN >32 ng/mL (80 nmol/L) (13). Previous groups have looked at the effects of various vitamin D supplementation regimens in preterm infants, many of which have not shown significant changes in infant 25(OH)D concentrations, but have shown that higher supplementation leads to improved length, head circumference, and possibly immune function (17). Previous studies have shown safety of increased vitamin D supplementation with 800 IU and 1000 IU without significant toxicity (18-20).

In a previous randomized control trial performed at this institution by [name] and colleagues, maternal supplementation with 6400 IU/day of vitamin D₃ was more effective in achieving

vitamin D sufficiency in mothers without increased risk to infants or mothers (21, 22). This present pilot study plans to replicate this in mothers and their preterm infants (22). See IRB application attachments for this paper that is *in press*.

To our knowledge, there are no studies specifically investigating maternal vitamin D supplementation on preterm infant vitamin D status. There has been investigation into maternal vitamin D supplementation on term infant vitamin D stores and data does suggest increased infant serum 25(OH)D levels with increased maternal supplementation (21, 23, 24). The objective of this study is to not only improve preterm infant vitamin D status but also maternal vitamin D status, as this continues to be an area of need in the Charleston, SC area.

The proposed pilot study will aim to improve 25(OH)D concentrations in mothers and their preterm infants, and therefore, allow us to further investigate and understand effects of maternal supplementation in preterm infants.

3.0 Intervention to be studied

Cholecalciferol or vitamin D₃ is an FDA approved medication for treatment and prevention of hypovitaminosis D.

Per Lexicomp, "Dosing: Adult

Note: 1 mcg = 40 units

Hypoparathyroidism (off-label use): Note: Active vitamin D preparations (ie, alfacalcidol, calcitriol) in conjunction with calcium supplementation are recommended therapy. Addition of cholecalciferol (or ergocalciferol) may be considered for supplemental therapy (25).

Osteoporosis, prevention (off-label use): Adults \geq 50 years of age: Oral: 800 to 1,000 units/day is recommended, through dietary sources and/or supplementation if needed (26).

Vitamin D insufficiency/deficiency treatment (off-label use): Note: Repletion strategies may vary depending on desired target serum 25(OH)D levels as well as the clinical status of the patient. The optimal serum 25(OH)D level is controversial; the Institute of Medicine recommends a 25(OH)D level >20 ng/mL (50 nmol/L) as sufficient in nearly all persons (27), whereas others have suggested targeting a level of ~ 30 ng/mL (75 nmol/L) to minimize the risk of fractures, particularly in patients with osteoporosis (28); (26). During pregnancy, the conversion of 25(OH)D to 1,25(OH)₂D, the active hormone of vitamin D is optimized at 40 ng/mL (100 nmol/L) and greater. However, some data suggest levels >40 ng/mL (>100 nmol/L) (median level in one trial: ~ 48 ng/mL) are associated with increased risk of falls in postmenopausal women (29, 30).

Therefore, some experts recommend a range of 20 to 40 ng/mL (50-100 nmol/L) as a reasonable target in most patients (31). In patients with normal absorption, for every 100 units/day of cholecalciferol, the serum 25(OH)D concentration is expected to increase by ~ 0.7 to 1 ng/mL (1.75 to 2.5 nmol/L) after a few weeks (32); (31). The dose-response declines as the 25(OH)D concentration increases above 40 ng/mL (100 nmol/L) (31). The following recommendations are based primarily on expert opinion and clinical experience:

Initial dosing (according to baseline serum 25(OH)D level):

Serum 25(OH)D 20 to 30 ng/mL (50 to 75 nmol/L): Initial: Supplementation dosing: Oral: 600 to 800 units once daily; a repeat serum 25(OH)D concentration is not required (31) **or** 1,000 to 2,000 units once daily; may consider a repeat serum 25(OH)D concentration in ~ 3 months to determine if the target level has been achieved (33).

Serum 25(OH)D 10 to <20 ng/mL (25 to 50 nmol/L): Initial:

Supplementation dosing: Oral: 800 to 1,000 units once daily (31) **or** 2,000 units once daily (33); a repeat serum 25(OH)D level should be drawn after ~3 months. If target serum 25(OH)D level has not been achieved, may increase to 2,000 units once daily or administer therapeutic dosing of 50,000 units once weekly for 6 to 8 weeks (31).

OR

Therapeutic dosing (ie, high-dose cholecalciferol): Oral: 50,000 units once **weekly** (or 5,000 to 7,000 units once **daily**) for ~8 weeks, followed by decreased maintenance dosing as needed to maintain target serum 25(OH)D level (34); (26).

Serum 25(OH)D <10 ng/mL (< 25 nmol/L) or in patients with deficiency symptoms: Initial Therapeutic dosing (ie, high-dose cholecalciferol): Oral: 50,000 units once **weekly** (or 5,000 to 7,000 units once **daily**) for 6 to 8 weeks to achieve target serum 25(OH)D level; a repeat serum 25(OH)D level should be drawn after ~3 months to assure target serum 25(OH)D level has been met (34); (31);(26).

Maintenance dosing: Maintenance dosing is highly patient specific and dependent on target 25(OH)D level, and may range from: 600 to 800 units/day (31) to 1,000 to 2,000 units/day (34);(26).

Special populations (obese patients, patients on medications known to affect vitamin D metabolism, patients with malabsorption syndromes or gastrectomy): Higher doses or longer durations may be necessary for adequate repletion (34); (31).

Vitamin D deficiency/insufficiency in patients with chronic kidney disease (off-label use): Oral:

Note: In patients without severe and progressive hyperparathyroidism, including chronic kidney disease stages G3 to G5 and dialysis or transplant patients, KDIGO guidelines recommend correcting vitamin D deficiency and insufficiency with treatment strategies recommended for the general population using cholecalciferol (or ergocalciferol) while avoiding hypercalcemia and ensuring phosphate levels are in the normal range. An individualized monitoring approach to direct treatment is also recommended (35);(36). In patients in whom serum parathyroid hormone levels are progressively rising and remain persistently elevated despite correction of modifiable factors (eg, hyperphosphatemia, vitamin D deficiency), calcitriol or vitamin D analogs are suggested instead of cholecalciferol (or ergocalciferol) (37).

Dosing: Geriatric

Refer to adult dosing.

Dosing: Renal Impairment: Adult

There are no dosage adjustments provided in the manufacturer's labeling

Dosing: Hepatic Impairment: Adult

There are no dosage adjustments provided in the manufacturer's labeling.

Dosing: Pediatric**Vitamin D deficiency, prevention (eg, Rickets prevention): AAP (14); (38):**

Oral:

Breastfed infants (fully or partially): Oral: 400 units/day beginning in the first few days of life.

Continue supplementation until infant is weaned to $\geq 1,000$ mL/day or 1 qt/day of vitamin D-fortified formula or whole milk (after 12 months of age)

Formula-fed infants ingesting $< 1,000$ mL of vitamin D-fortified formula: Oral: 400 units/day

Children and Adolescents without adequate intake: Oral: 400 to 600 units/day. **Note:** Children with increased risk of vitamin D deficiency (chronic fat malabsorption, maintained on chronic antiseizure medications) may require higher doses; use laboratory testing [25(OH)D, PTH, bone mineral status] to evaluate

Vitamin D deficiency, treatment: Oral: **Note:** Treatment should also include calcium and phosphorus supplementation; some patients with chronic fat malabsorption, obesity, or who are maintained on chronic antiseizure medications, glucocorticoids, HIV medications, or antifungals may require higher doses of cholecalciferol (39); monitor vitamin D status closely.

Infants: Oral: 2,000 units daily for 6 weeks to achieve a serum 25(OH)D level > 20 ng/mL (> 50 nmol/L); followed by a maintenance dose of 400 to 1,000 units daily. **Note:** For patients at high risk of fractures a serum 25(OH)D level > 30 ng/mL (75 nmol/L) has been suggested (39).

Children and Adolescents: Oral: 2,000 units daily for 6 to 8 weeks to achieve serum 25(OH)D level > 20 ng/mL (> 50 nmol/L); followed by a maintenance dose of 600 to 1,000 units daily. **Note:** For patients at high risk of fractures a serum 25(OH)D level > 30 ng/mL (> 75 nmol/L) has been suggested (39).

Vitamin D deficiency in cystic fibrosis, prevention and treatment: Oral:

CF guidelines (40):

Recommended initial daily intake to maintain serum 25(OH)D level ≥ 30 ng/mL (> 75 nmol/L):

Infants: Oral: 400 to 500 units/day

Children ≤ 10 years: Oral: 800 to 1,000 units/day

Children > 10 years and Adolescents: Oral: 800 to 2,000 units/day

Dosing adjustment for serum 25(OH)D level between 20 to 30 ng/mL (50 to 75 nmol/L) and patient adherence established (Step 1 increase):

Infants: Oral: 800 to 1,000 units/day

Children ≤ 10 years: Oral: 1,600 to 3,000 units/day

Children > 10 years and Adolescents: Oral: 1,600 to 6,000 units/day

Dosing adjustment for serum 25(OH)D level < 20 ng/mL (< 50 nmol/L) or persistently between 20 to 30 ng/mL (50 to 75 nmol/L) and patient adherence established (Step 2 increase):

Infants: Increase up to a maximum 2,000 units/day

Children ≤ 10 years: Increase to a maximum of 4,000 units/day

Children >10 years and Adolescents: Increase to a maximum of 10,000 units/day

Alternate dosing (41):

Initial dose: Serum 25(OH)D level \leq 30 ng/mL (\leq 75 nmol/L)

Infants: Oral: 8,000 units/**week**

Children and Adolescents: Oral: 800 units/day

Medium-dose regimen: Serum 25(OH)D level remains \leq 30 ng/mL (\leq 75 nmol/L) and patient compliance established

Infants and Children <5 years: Oral: 12,000 units/week for 12 weeks

Children \geq 5 years and Adolescents: Oral: 50,000 units/week for 12 weeks

High-dose regimen: Repeat 25(OH)D level remains \leq 30 ng/mL (\leq 75 nmol/L) and patient compliance established

Infants and Children <5 years: Oral: 12,000 units twice weekly for 12 weeks

Children \geq 5 years and Adolescents: Oral: 50,000 units twice weekly for 12 weeks

Vitamin D insufficiency or deficiency associated with CKD (stages 2 to 5, 5D), treatment; serum 25 hydroxyvitamin D [25(OH)D] level \leq 30 ng/mL (\leq 75 nmol/L) (42): Oral:

Serum 25(OH)D level 16 to 30 ng/mL (40 to 75 nmol/L): Infants, Children, and Adolescents: 2,000 units/day for 3 months or 50,000 units every month for 3 months

Serum 25(OH)D level 5 to 15 ng/mL (12.5 to 37.5 nmol/L): Infants, Children, and Adolescents: 4,000 units/day for 12 weeks or 50,000 units every other week for 12 weeks

Serum 25(OH)D level <5 ng/mL (< 12.5 nmol/L): Infants, Children, and Adolescents: 8,000 units/day for 4 weeks then 4,000 units/day for 2 months for total therapy of 3 months or 50,000 units/week for 4 weeks followed by 50,000 units 2 times/month for a total therapy of 3 months

Maintenance dose [once repletion accomplished; serum 25(OH)D level $>$ 30 ng/mL ($>$ 75 nmol/L)]:
Infants, Children, and Adolescents: 200 to 1,000 units/day

Nutritional rickets, treatment: Limited data available (38): Administer in combination with calcium supplementation:

Daily therapy (preferred):

Infants: Oral: 2,000 units daily for \geq 3 months, followed by maintenance dose of 400 units daily

Children: Oral: 3,000 to 6,000 units daily for \geq 3 months, followed by maintenance dose of 600 units daily

Adolescents: Oral: 6,000 units daily for \geq 3 months, followed by maintenance dose of 600 units daily

Single-dose therapy:

Infants \geq 3 months: Oral: 50,000 units once, or in divided doses over several days; after 3 months, initiate maintenance dose of 400 units daily

Children: Oral: 150,000 units once, or in divided doses over several days; after 3 months, initiate maintenance dose of 600 units daily

Adolescents: Oral: 300,000 units once, or in divided doses over several days; after 3 months, initiate maintenance dose of 600 units daily

Dosing: Renal Impairment: Pediatric

There are no dosage adjustments provided in the manufacturer's labeling; however, cholecalciferol is not renally eliminated to a significant extent and dosage adjustment is not necessary.

Dosing: Hepatic Impairment: Pediatric

There are no dosage adjustments provided in the manufacturer's labeling.

Use: Labeled Indications

Dietary supplement: As a vitamin D dietary supplement

Doses for this study are under IND 66,346 and it's safety has been proven in this referenced study that is currently *in press* in Breastfeeding medicine (22).

Maternal and infant placebos will be used in this study. Maternal placebo will be sugar gummies from the same manufacturer (Church & Dwight). Infant placebo vitamin D drops will be from the same company (D Drops) and contain the eluent without the vitamin D.

4.0 Study Endpoints

- Primary outcomes will be:
 - Infant total circulating 25(OH)D concentration at 3 months
 - Mother total circulating 25(OH)D concentration at 3 months
- Primary or secondary safety endpoints
 - Maternal serum calcium concentration initially and at months 1-, 2-, and 3
 - Maternal urine calcium/creatinine ratios initially and at months 1-, 2-, and 3
 - Infant serum calcium concentration at time points initially and at months 1-, 2-, and 3

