3. Daily Vitamin D Supplementation: Infants of mothers who receive 600 IU of vitamin D₃ will receive 400 IU of vitamin D₃ in the form of drops. Infants of mothers who receive 6600 IU of vitamin D₃ will receive placebo drops.

3. General Health Assessment of Infant: At 1 week after delivery and then monthly until 3-months of age, each enrolled infant will undergo a growth (measuring head circumference, weight, length, head circumference, Ponderal index, body mass index [BMI]) and general health assessment.

4. PEAPOD Assessment: Prior to discharge from the NICU, the infant will also be placed in the PEAPOD® for body mass composition analysis. The material and data will be specifically obtained for research purposes. There is minimal risk. This is a safe device in which the infant lays in for 2 minutes.

5. Blood Sample from Infant: At initial visit, 1-, 2- and 3-months of age, each infant will have a blood sample 4mL (<1tsp) taken from either a vein (infant’s hand, arm or foot) or the heel. Total amount obtained will be less than 12mL (<1 1/2 tablespoon). The serum sample will be analyzed for vitamin D and calcium concentration. Parents will be counseled that if their infant is vitamin D deficient, the infant’s primary care physician and they will be contacted regarding the finding(s) with recommended follow-up.

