C. Interim Data Analyses & Monitoring: Interim analyses for the evaluation of safety and efficacy will be conducted based on the recommendations of the Data Safety & Monitoring Board for two reasons: more than 10% of subjects in a given arm had achieved urinary calcium/creatinine ratios outside the acceptable range or there is evidence to the DSMC that there is significant clinical benefit to a given treatment arm over the other arm or arms of the study. The DSMC will serve to monitor for safety and efficacy. DSMB reports will include summary statistics: on mother-child recruitment (expected vs. actual); mother-child follow-up visits (expected vs. actual); data form quality (completion and timeliness of forms); tracking of data editing; demographics of the randomized mothers-children; aggregate safety; aggregate efficacy; and related information. The DSMB also will monitor the trial from the standpoint of futility using the techniques of Lan and Wittes (43).

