hypercalciuria and hypercalcemia. There is a small risk that the woman's blood calcium level would increase in response to higher dose vitamin D supplementation. The body responds by excreting calcium in the urine to maintain normal calcium levels. If calcium levels in the blood continue to rise, then serum calcium will increase leading to hypercalcemia. This process takes weeks to months to occur. It takes approximately 3 months to reach steady state on an increased vitamin D intake/regimen. In related studies conducted at MUSC comparing maternal vitamin D supplementation with 400, 2400, or 6400 IU of vitamin D₃/day and their infants for 7 months, there were no differences in infant or maternal safety parameters (22). There were no reported episodes of either hypercalciuria or hypercalcemia in any of the treatment groups. In fact, maternal 25 (OH)D levels were higher in the 6400 IU/day treatment group compared to the 400 IU group. In breastfed infants, there was no statistical difference in the average circulating 25 (OH)D in either treatment arm (22).

- a. To ensure that each lactating mother and her breastfeeding infant and each nonlactating mother (and her formula-feeding infant as a control) maintain normal vitamin D status throughout the study period and not develop hypervitaminosis D, both mother and infant will be screened monthly for hypercalciuria, the first indicator of hypervitaminosis D. All study subjects will be monitored closely for hypervitaminosis D. Operationally, we define caution limits as urinary Ca/creatinine ratio > 0.8 mmol/mmol. Whenever any patient

exceeds the caution limit, a specific case study will be initiated by the Data Safety and Monitoring Committee (DSMC) to examine the contribution of sunlight exposure and other confounding factors. Operationally, we define upper limits as a urinary calcium/creatinine ratio > 1.0 mmol/mmol Ca/creatinine ratio. This is a conservative upper limit as circulating levels achieved in individuals living in sun-rich environments achieve this amount without causing toxicity. The DSMC will be convened to review any patient who exceeds any predefined toxic limit for any outcome. If the elevated levels are unexplained, the patient will be withdrawn from supplementation but will continue to be monitored.

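### H3 claims no health consequences for the infant relative to infant supplementation, but safety is assessed case by case, the only infant safety endpoint is serum calcium, and no arm comparison of growth or infant adverse events is stated

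*Protocol*

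**What the plan says.** **The claim.** H3 in Section 1.0 compares the two regimens. Maternal high-dose supplementation is expected to be safe and more effective than supplementing the infant alone, "without any adverse side effects or health consequences in the mother or infant". On the infant side the contrast is real: Group A infants receive 400 IU/day, and "Those infants of lactating mothers assigned to Group B will receive placebo".

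**How safety is assessed.** Aim 1 states: "Safety will be assessed throughout the study on a case-rather than a treatment arm basis". The cautionary levels it names are maternal urinary calcium/creatinine and serum calcium in mother and infant.

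**The endpoints.** Section 4.0 lists three safety endpoints: two maternal, and for the infant "Infant serum calcium concentration at time points initially and at months 1-, 2-, and 3". Infant 25(OH)D at 3 months is a primary outcome.

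**Other infant data.**
- Section 10.0: "At 1 week after delivery and then monthly until 3-months of age, each enrolled infant will undergo a growth", and the same sentence adds a general health assessment. Its questionnaire table includes Infant Health/Diet (Q8) and Maternal/Infant Health Assessment (Q9).
- Section 10.0, infant blood sample: if an infant is deficient, the parents are told that the "primary care physician and they will be contacted regarding the finding(s) with recommended follow-up".
- Section 13.0: adverse events are reviewed quarterly, and monitoring board reports include aggregate safety.
- Section 15: mother and infant are "screened monthly for hypercalciuria, the first indicator of hypervitaminosis D", and infants below 20 ng/mL at visit 4 are supplemented.

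**Arm-level triggers.** Section 13.0 C gives two reasons for an interim analysis. One is that "more than 10% of subjects in a given arm had achieved urinary calcium/creatinine ratios outside the acceptable range". The other is evidence of a clinical benefit of one arm over another, which is not tied to calcium.

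**The concern.** A claim that one regimen does no harm relative to another needs outcomes compared between the regimens. A case-level rule answers a different question, namely whether this infant should stop. If average growth were somewhat lower in one arm, no infant need cross an individual limit.

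The numerical safety limits in the protocol mostly concern calcium excess. In Group B the infant's own dose is withheld, so under-supply is a possible harm too. The protocol covers that biochemically through 25(OH)D, but 25(OH)D is not itself a health consequence. Section 2.0 reports that higher dosing of preterm infants has been associated with better length and head circumference, which makes growth a relevant outcome here.

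At stake is the infant safety conclusion. A report could state that H3 was borne out when only serum calcium and 25(OH)D had been set out beforehand as infant outcomes.

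**Working it through.** The protocol gives no figure for this point, so there is none to reproduce. The first step sets the text side by side. The second sizes what an added comparison could deliver.

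**Step 1. Scope of the claim against what is stated.**

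| Infant item | Collected or monitored | Endpoint in Section 4.0 | Arm comparison of growth or adverse events stated |
|---|---|---|---|
| Serum calcium | Yes | Yes, safety | Not applicable |
| 25(OH)D | Yes | Yes, primary | Not applicable |
| Growth | Yes, 1 week and months 1, 2, 3 | No | No |
| General health assessment, Q8, Q9 | Yes | No | No |
| Adverse events | Yes, quarterly review and aggregate reports | No | No |

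The one analysis stated for an infant body measure is Aim 2's search for correlations between body composition, diet, milk and vitamin D status. That is not a comparison of arms. H3 covers every row of the table; the stated infant endpoints cover the first two.

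**Step 2. Precision of a growth comparison.** Inputs:
- n = 25 per arm (Section 6.0).
- Growth in SD units at month 3.
- Correlation r between the 1-week and month-3 values. The protocol gives none, so r = 0.3, 0.5 and 0.7 are assumptions.
- The 1-week value is treated as a baseline, since randomisation is 3 to 7 days after delivery.

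Unadjusted 95% half-width: t(0.975, 48) × √(2/25) = 2.011 × 0.2828 = **0.57 SD**.

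Adjusted: t(0.975, 47) × √(2/25) × √(1 − r²) = 2.012 × 0.2828 × √(1 − r²):
- r = 0.3: **0.54 SD**
- r = 0.5: **0.49 SD**
- r = 0.7: **0.41 SD**

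With an assumed 20 per arm after dropout, the unadjusted figure is 2.024 × √(2/20) = 0.64 SD. The adjusted figures are 0.61, 0.56 and 0.46 SD.

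The difference detectable with 80% power (two-sided 5%, 25 per arm) is about 0.81 SD unadjusted and 0.70 SD at r = 0.5.

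**Step 3. Adverse events.** If none of 25 infants in an arm had a given event, the exact two-sided 95% upper limit would be 1 − 0.025^(1/25) = 1 − 0.863 = 13.7%. Even a clean result does not amount to an absence of consequences.

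**The case against.** The best case for leaving the text alone has four parts.

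1. *Section 4.0 is not exhaustive.* Milk composition and infant body composition are stated Aim 2 analyses and are also absent from it, so absence does not prove that growth will go unanalysed. This stands. The point is therefore that no arm comparison is stated, not that none will be made.

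2. *Infant health is captured more widely than by calcium.* The general health assessment, Q8 and Q9, and adverse event review fit H3's wording at least as closely as growth does. This also stands, and it is why the fix covers adverse events as well as growth. None of these sources, however, is tied in the protocol to a comparison of the infants by arm, and Aim 1 says that safety is judged by case.

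3. *A descriptive growth estimate cannot support a no-harm conclusion either.* Correct, given the widths above. Adding growth does not rescue the broad claim, so H3 has to be narrowed first.

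4. *Analysis detail can sit in a statistical analysis plan.* True of scaling and tabulation. The mismatch lies between a hypothesis and an endpoint list that the protocol itself fixes.

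A reader might go further and infer three things that the protocol does not support:
- *That infants are monitored only for calcium.* Section 10.0 provides for reporting deficiency, Section 13.0 for adverse event review, and Section 15 for hypercalciuria screening and supplementation at visit 4.
- *That urinary calcium/creatinine is the only arm-level trigger.* The clinical-benefit trigger in Section 13.0 C is not limited to calcium, although it sets no growth threshold.
- *That Group B infants are expected to grow less.* The Section 2.0 evidence concerns direct infant dosing and predicts no deficit when the mother is dosed instead.

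**Conclusion.** The concern holds in a limited form. H3's infant statement is wider than the outcomes through which the protocol says it will be examined, and the case-level rule in Aim 1 cannot answer a claim about regimens. With the stated endpoints, the infant conclusion can rest on serum calcium and 25(OH)D.

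The pilot's size also rules out the broad statement. A growth difference would be estimated to within about ±0.57 SD unadjusted, or ±0.41 to ±0.54 SD adjusted, so a moderate deficit could not be excluded. These widths assume 25 evaluable infants per arm; the adjusted ones also rest on assumed correlations. Dropout would widen them.

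This should be changed, but it is not critical: the primary 25(OH)D conclusion does not depend on it, and the growth data are already scheduled.

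**What to change.** 1. **Section 1.0, H3.** Limit the infant safety conclusion to the outcomes compared between arms, and do not conclude from a 50-dyad pilot that there are no health consequences.
2. **Section 4.0.** Add infant weight, length and head circumference at month 3, adjusted for the 1-week value, and infant adverse events, as secondary safety outcomes. Report them by arm with 95% confidence intervals, label them descriptive, and make no claim of no difference. Standardising growth for sex and postmenstrual age would be sensible; that detail can go in the analysis plan.
3. **Section 1.0, Aim 1.** Say that the case-level limits are the individual stopping rule and do not replace the comparison by arm.

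**Cost.** Wording in two sections, three growth estimates and one adverse event summary from data already planned, with no new visit or procedure. The downside is a weaker H3 and wide intervals, which should be reported as such.
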